- 9- Even if such collaboration is effective, it may not be scalable due to a limited number of geriatric healthcare providers.

As a result, an automated geriatric co-management program, if shown to be feasible and as effective as in-person geriatric co-management, could be used to provide peri-operative geriatric care routinely in institutions that have limited or no geriatrics services.

The Electronic Rapid Fitness Assessment (the eRFA) at Memorial Sloan Kettering Cancer Center (MSKCC)

The eRFA was developed at MSKCC through collaboration between the Geriatrics Service and the Web Survey Core Facility (Webcore) in 2015. During the eRFA development process, the Geriatrics Service held multiple discussions to determine which GA domains to assess and which validated assessment methods to use. The name “Electronic Rapid Fitness Assessment” was selected to reflect the purpose of the GA, which is to distinguish patients who are fit from those who are frail.

Administration and Reporting of the eRFA:

The eRFA was first implemented in the Geriatrics clinic. In 2016, the Thoracic surgery clinic implemented the eRFA at the point of care. All patients who present to MSKCC geriatric clinics or thoracic surgery clinics complete the eRFA while they are waiting to be seen by their healthcare providers for their initial consultation. Patients may complete the eRFA on their own or with assistance from others (e.g., a caregiver), or they may allow someone else

(e.g., a caregiver) to complete the assessment for them. Patients may also complete the eRFA at home, before their appointment, if they have Internet access and an e-mail account. After the assessment has been completed, a registered nurse (RN) performs a cognitive assessment using the Mini-Cog[17, 18] and establishes the patient's mobility using the Timed Up and Go (TUG)[19] test, the results of which are then entered into the eRFA by the RN. The Mini-Cog and TUG assessments will be omitted if the patient is being seen via telemedicine.

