	Timed Up and Go test [19]	Nurse	Patients are asked to stand from the chair, walk ten feet, turn and return to the chair. The total time is recorded.	<10 seconds, 10-19 seconds, ≥ 20 seconds	≥ 10 seconds
Social support/activity	Social support survey [23]	Patient	The Medical Outcome Study- Social Support Survey- 4 item asks 4 questions on how often patients have someone to receive support from: All the time (5), Most of the time (4), Some of the time (3), A little of the time (2), Not at all (1). Higher scores mean better social support.	4-20	≤ 16
	Social activity limitation [24]	Patient	The Medical Outcome Study- Social Activity Survey asks how much patients' social activity is limited and how much often it has become limited/ interfered with recently. 3 questions with 5 answers (1-5) are counted. Higher scores mean more limited social activity.	3-15	≥ 8
Cognition	Mini Cog test [17, 18]	Nurse	Patients are told three words to memorize. Then they are asked to draw a clock with hands showing ten past eleven. Then they are asked to recall the three words. Clock draw is evaluated either normal with 2 points or abnormal with 0 point. Each correctly recalled word has 1 point (0-3).	0-5	≤ 2

Emotional wellbeing	Distress [25]	Patient	The Distress Thermometer ranges from 1 (no distress) to 10 (extreme distress).	1-10	≥ 4
	Depression [26, 27]	Patient	The Geriatric Depression Scale- 4 item is a yes/no questionnaire. Patients receive 1 point for each answer that indicates depression.	0-4	≥ 1
Poly-pharmacy	Poly-pharmacy [28]	Patient	The number of medications currently taken	1-4 medications, 5-9 medications, ≥ 10 medications	≥ 5 medications
Nutritional status	Weight change	Patient	Weight change in the past 6 months	no change or weight gain, lost < 5 lbs, lost 5-10 lbs, lost 10-20 lbs, lost ≥ 20 lbs	lost ≥ 10 pounds

The eRFA in the Thoracic Surgery Clinics as a Model for other Surgical Clinics:

After development and successful implementation of the eRFA in all MSKCC Geriatric clinics[29], more than 4000 older cancer patients with a median age of 80 have completed the eRFA. Patients have shown very high levels of satisfaction with the instrument, and, as a result, thoracic surgery clinics have implemented the eRFA in their clinics as a routine care for the new patients. We have shown that implementation of eRFA in the thoracic surgery clinics is feasible and can yield useful clinical information that can be managed perioperatively.[30]

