Following completion of the eRFA, the summary of impairments as well as the recommendations generated by the study team (hard-copy or email) will be provided in real-time to the thoracic surgery team for their attention. A sample is provided below. In this case, patient has impairments in various domains that ranges from KPS to number of medications.

[eRFA Summary](#)

Global recommendation: If 3 or more impairments are listed in the summary below, consider referral to geriatrics.
T = Threshold | **P** = Percentile | **PS** = Patient Score

KPS  More Information:	T: ≤ 80	P: 37%	PS: 60.
ADL  More Information:	T: < 14	P: 52%	PS: 12.
iADL  More Information:	T: < 16	P: 45%	PS: 13.
Timed Up and Go Test  More Information:	T: ≥ 10 seconds	P: 36%	PS: 10-19 seconds.
Social Support  More Information:	T: ≤ 16	P: 43%	PS: 16.
Limited Social Activity  More Information:	T: ≥ 8	P: 50%	PS: 12.
Weight Change  More Information:	T: 10 pound loss or more	P: 16%	PS: 10-20.
Distress Level  More Information:	T: ≥ 4	P: 55%	PS: 7.
Number of Medications  More Information:	T: ≥ 5	P: 45%	PS: More than ten.

Subsequently, the research staff member clicks on various impairments and would be able to view and print the recommendations for each impairment. For example, the following are the recommendations for a Timed Up and Go test impairment.

Timed Up and Go Test **T:** ≥ 10 seconds **P:** 36% **PS:** 10-19 seconds.

[More Information:](#)

[Pre/Postop Recommendation:](#)

- A- Consider consultation with physical therapy and occupational therapists.
- B- Encourage use of appropriate assistive devices.
- C- Encourage resistance exercises such as repeated chair stand in the preoperative period.
- D- Consider use of stationary bike or bike pedals in the preoperative period.

[Medical Recommendation:](#)

[Education:](#)

[Supportive Services:](#)

A copy of the recommendations will be available in EMR. After preoperative clearance by patients' primary care providers, general internal medicine service, or other services such as cardiology, patients will undergo surgery. The geriatrics service will see patients before or after surgery if the consult is requested by the surgery service. The automated co-management program is not expected to lengthen the patients' first visits.

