7.1 ASSESSMENT/EVALUATION PLAN

Assessment and Measurement Instruments:

In this study, the data will be collected using the following instruments and measurements methods:

- Electronic Medical Record review:

- 1- For patients in the intervention group (automated geriatric co-management), we will assess the percentage of recommendations that were followed by the surgery team. For example, if automated geriatric co-management recommends consultation with physical therapy perioperatively, we will assess whether the consult has been obtained.
- 2- For patients in both groups, we will assess the adverse surgical events by day 30 following surgery. Adverse surgical event is a composite of surgical complications grade 2 or higher, mortality after surgery, or discharge to any place other than home, or prolonged length of stay (defined as length of stay longer than 75% of the cohort who underwent the same surgical procedure), or readmission to the hospital within 30 days from surgery.

MSKCC's secondary surgical events database in the EMR has been shown to accurately record major postoperative complications within the 30 days after surgery[34].

- 3- to assess sociodemographic characteristics (age, gender, ethnicity),
- 4- to assess routine preoperative blood work (complete blood cell counts, chemistry panel).
- 5- To assess cancer characteristics (stage, receipt and type of neoadjuvant treatment)

- 6-** To assess surgical characteristics (type of surgery: minimally invasive vs open, duration of surgery, intraoperative blood loss, and American Society of Anesthesiologist Physical Status classification)
- **Four Meter Walk Test:** In order to assess functional recovery, the 4-meter walk test will be performed. In the 4-meter walk test, the time that it takes patients to walk 4 meters in their usual pace will be recorded in seconds by the clinical research staff. (This portion will be skipped for patients being seen via telemedicine.)

Assessment and Evaluation Plan

Patients will be screened for study eligibility at the time of attending their surgery appointment at MSKCC for consideration of surgery. The inclusion and exclusion criteria will be reviewed by the clinical research staff firstly to confirm the patients' eligibility status. Once eligibility has been determined and informed consent has been obtained, patients will undergo baseline assessments and subsequently randomization will occur.

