We are additionally interested in using the three components, of the patient-reported functional recovery in three categories: complete recovery (defined as all three post-operative measurement score being greater than or equal to the pre-operative measurement score), partial recovery (defined as at least one, but not all three, post-operative measurement scores being greater than or equal to the pre-operative measurement score), or no recovery (defined as none of the post-operative measurement scores being greater than or equal to the pre-operative measurement score). Similarly we will use two components of the clinician-evaluate functional recovery to define three categories: complete recovery (defined as all both post-operative measurement score being greater than or equal to within 10% of the pre-operative measurement score), partial recovery (defined as at least one, but not both, post-operative measurement scores being greater than or equal to within 10% of the pre-operative measurement score), or no recovery (defined as neither of the post-operative measurement scores being greater than or equal to within 10% of the pre-operative measurement score). We will test the association between intervention arm and degree of recovery by using ordinal regression with randomization strata as covariates.

As it is likewise plausible that the relative value of in-person vs. automated geriatric co-management depends on baseline risk, we will repeat the analysis described above, related to baseline risk, for the outcomes of patient-reported functional recovery and clinician-assessed functional recovery.

Sample size

With a null hypothesis of 55% and the alternative hypothesis of 70% of patients with recommendations followed, and a one-sided α of 5% and a power of 85%, we require 77 eligible patients to be accrued in the automated geriatric co-management arm for a two-stage Simon minimax design. We expect about 25% of patients to be excluded for the primary aim due to no impairment (5%) or crossover to the in-person

geriatric comanagement arm (20%) suggesting a total accrual close to 100 per group.

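### The clinician-evaluated recovery categories run the wrong way for two tests scored as times: read literally, a slower patient counts as recovered

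*Combined protocol and SAP*

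**What the plan says.** Section 11.0, under functional recovery, names the TUG and the 4MWT as the two clinician-evaluated measures and restricts their analysis to patients assessed in person. Each is compared between arms by ANCOVA. The plan then adds a three-level outcome built from both tests. The top level is "complete recovery (defined as all both post-operative measurement score being greater than or equal to within 10% of the pre-operative measurement score". The middle level is "at least one, but not both, post-operative measurement scores being greater than or equal to within 10" per cent of the pre-operative value, and the lowest is "no recovery (defined as neither of the post-operative measurement scores being greater than or equal to within 10% of the pre-operative measurement score". The levels go into an ordinal regression by arm with the randomization strata, which is repeated by baseline risk.

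On the scale of the tests:

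- 4MWT (section 7.1): "the time that it takes patients to walk 4 meters in their usual pace will be recorded in seconds".
- TUG (section 3.1, Figure 2): the description says "The total time is recorded", the score range is given as "<10 seconds, 10-19 seconds, ≥ 20 seconds", and 10 seconds or more is the frail value.
- The nurse performs the TUG and the Mini-Cog, "the results of which are then entered into the eRFA by the RN" (section 3.1). The sample report in section 4.2 shows the patient's TUG score as a band: "PS: 10-19 seconds".

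**The concern.** The wording follows the patient-reported rule just before it. That rule is right for Karnofsky status, bADL and iADL, where a higher score is better. On a timed test a higher value is worse, so the same inequality rewards slowing. The documents do not convert walk time to speed, reverse-code either test, or say that greater means better. The direction-neutral definition (the same or better) is given for Karnofsky status only.

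Coded as written, the ordinal regression and its baseline-risk repeat could favour the arm that slowed more and contradict the plan's own ANCOVA of the same two tests. If the analyst notices, a replacement rule has to be chosen after the plan is fixed, possibly with data in hand.

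The TUG scale is a related gap. The documents do not say whether seconds or the three bands are analysed, and a 10% tolerance has no clear meaning on three bands.

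**Working it through.** No sample size, power or alpha in the plan depends on this rule, so there is no stated figure to reproduce. The check has two parts: what the rule does to single patients, which needs no assumptions, and an illustration of what it does to an arm comparison, which does.

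**1. The rule as an inequality.** Let T be the time on a test.

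- As written: T_post ≥ 0.90 × T_pre.
- Two-sided reading (within 10% either way): 0.90 × T_pre ≤ T_post ≤ 1.10 × T_pre.
- Direction corrected, same tolerance: T_post ≤ 1.10 × T_pre.

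**2. Single patients, in seconds.** For a pre-operative 4MWT of 5 s the limits are 0.90 × 5 = 4.5 s and 1.10 × 5 = 5.5 s. For a pre-operative TUG of 12 s they are 10.8 s and 13.2 s.

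| Test, pre to post | As written | Two-sided | Corrected |
|---|---|---|---|
| 4MWT 5 to 10 s (slower) | meets | fails | fails |
| 4MWT 5 to 4 s (faster) | fails | fails | meets |
| TUG 12 to 18 s (slower) | meets | fails | fails |
| TUG 12 to 10.5 s (faster) | fails | fails | meets |

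**3. TUG in bands.** Code the bands in order of time and read the rule as post band ≥ pre band. A slower patient stays in the band or moves up and always meets it (12 to 18 s, 12 to 22 s, 8 to 12 s). A faster patient who stays in the band meets it (12 to 10.5 s). One who drops a band fails it (12 to 9 s, 25 to 15 s). So slowing passes on either TUG scale, while improvement is penalised in seconds, or in bands only when a band is crossed.

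**4. Illustration for arms.** Assumed, because the documents give no spread, correlation or expected slowing: log(T_post/T_pre) is normal on each test with SD 0.15, the correlation between tests is 0.7, and both tests are in seconds. Complete means both tests meet the rule, and none means neither does. For a median ratio of 1.20:

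- As written, per test: z = (ln 1.20 − ln 0.90)/0.15 = 0.2877/0.15 = 1.92, probability 0.972. Both tests: 0.954.
- Corrected, per test: z = (ln 1.10 − ln 1.20)/0.15 = −0.0870/0.15 = −0.58, probability 0.281. Both tests: 0.175.

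Repeating this for an arm 10% slower, and fitting a proportional-odds model to the category probabilities, gives:

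| Rule | Arm 10% slower: complete / partial / none | Arm 20% slower: complete / partial / none | Odds ratio for better recovery, slower arm |
|---|---|---|---|
| As written | 86 / 10 / 4% | 95 / 4 / 1% | 3.4 |
| Corrected | 37 / 25 / 37% | 18 / 21 / 61% | 0.37 |
| Two-sided | 24 / 33 / 42% | 13 / 24 / 63% | 0.45 |

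**5. Sensitivity.**

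- Log-SD from 0.10 to 0.35, same contrast: 10.7 to 1.55 as written, 0.22 to 0.65 corrected, 0.23 to 0.86 two-sided.
- Smaller contrast, 15% v 20% slower: 1.87 as written v 0.61 corrected at log-SD 0.15, and 1.24 v 0.81 at log-SD 0.35.
- Other inputs (log-SD 0.2, correlation 0.5): at a mean log change of +0.2, 89% complete as written v 16% corrected. At −0.1 (improvement), 34% v 74%.
- TUG in bands, 4MWT in seconds (assumed baseline TUG median 8–15 s, log-SD 0.25–0.35): at 20% slower, about 96–97% complete as written v 25% corrected. For 10% v 20% slower the odds ratio is 3.3–3.4 v 0.41–0.42.
- Two-sided reading for a group that improves (median ratio 0.95, log-SD 0.15): 29% complete v 76% corrected, because patients more than 10% faster are failed.

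**6. Chance of a significant result for the slower arm under the written rule** (10,000 simulated trials, unstratified tie-corrected rank-sum test, two-sided 5%, log-SD 0.15). For 10% v 20% slower: 63% with 95 per arm and 32% with 40 per arm. For 15% v 20% slower: 17% and about 9–10%. The 95 is the plan's own number after dropout and is a ceiling here, since only patients assessed in person contribute. The 40 is assumed.

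**The case against.** The strongest reply is that nobody would code it this way. The levels are labelled as recovery, the phrase is garbled rather than a clean inequality, and a rule under which a patient who doubles their walking time has recovered is hard to miss. The intent is very probably as good or better, within 10%. That is fair, and it makes a reversed published result less likely. It does not settle the rule: an analyst who spots the problem still has to choose among several corrections, and the plan exists to make that choice in advance.

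Two kinder readings do not rescue the text:

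- Two-sided within 10%. This removes the reversal between arms in the example above, but it disregards half of the phrase and still classes a patient more than 10% faster as not recovered.
- Gait speed. The reference cited for the walk test mentions gait speed in its title, and on a speed scale the inequality points the right way. But section 7.1 records seconds and gives no conversion, and TUG would remain a time, so the two components would run in opposite directions.

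The objections on reach and size stand. This is a pilot, the categories supplement the ANCOVA, they use in-person assessments only, and a reversed result would visibly conflict with the ANCOVA. Every arm-level figure rests on assumed inputs, and with no difference between arms the rule creates none. The TUG scale is strictly a separate question from direction, but a corrected rule cannot be applied to TUG until it is answered.

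**Conclusion.** The concern holds. The criterion in all three clinician-evaluated categories points the wrong way for tests recorded as times. That conclusion follows from the text alone. On the 4MWT any slowing meets the criterion and any improvement of more than 10% fails it. On TUG any slowing also meets it, while improvement fails it by more than 10% if seconds are analysed, or on moving to a faster band if bands are.

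The size is illustrative. Under the assumptions above, the odds ratio changes from 0.37 to 3.4 for arms 10% v 20% slower, and the sign is wrong at each spread tried from log-SD 0.10 to 0.35. The consequence is confined to the ordinal regression of clinician-evaluated recovery and its repeat by baseline risk. The primary feasibility endpoint, the sample size, the patient-reported categories and the direction of the ANCOVA are untouched. It should be corrected before analysis, because functional recovery is a stated aim (Aim 3).

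**What to change.** Before analysis, replace the criterion in all three categories with one rule in the direction of the tests: recovery on a timed test means post-operative time ≤ 1.10 × pre-operative time. This keeps the plan's own 10% tolerance. If the team prefers speed for the 4MWT, speed ≥ 0.90 × pre-operative speed is time ≤ 1/0.90 = 1.11 × pre-operative time, which is nearly the same; the plan should state which one applies.

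Separately, check how TUG is stored and use one scale for everyone. If seconds are held for all patients, use seconds. Otherwise use bands for all, because seconds can be converted to bands but not the reverse. With bands, define TUG recovery as the same or a better band, and replace the TUG ANCOVA with an ordinal model adjusted for baseline band and strata. Do not mix the two scales within the endpoint.

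The cost is one corrected definition and one check of a data field, plus the change of TUG model if only bands are available. No new patients or procedures are needed. The downside is that, if seconds are missing for some patients already enrolled, using bands for everyone loses some TUG information and the 10% tolerance on that test.

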12.1 RESEARCH PARTICIPANT REGISTRATION AND RANDOMIZATION PROCEDURES

12.2 Research Participant Registration

Confirm eligibility as defined in the section entitled Inclusion/Exclusion Criteria. Obtain informed consent, by following procedures defined in section entitled Informed Consent Procedures. During the registration process registering individuals will be required to complete a protocol specific Eligibility Checklist. The individual signing the Eligibility Checklist is confirming whether or not the participant is eligible to enroll in the study. Study staff are responsible for ensuring that all institutional requirements necessary to enroll a participant to the study have been completed. See related Clinical Research Policy and Procedure #401 (Protocol Participant Registration).

12.3 Randomization

Randomization to either in-person geriatric co-management or automated geriatric co-managements will be accomplished by the method of randomly permuted blocks of random length. Patients will be stratified by planned procedure type (minimally-invasive surgery vs open surgery), age (65-74 vs. 75+) and baseline number of eRFA impairments (<4 vs. ≥ 4 : anticipated median number of eRFA impairments) Randomization will be conducted by use of the Clinical Research Database (CRDB) at MSKCC.

13.1 DATA MANAGEMENT ISSUES

MSKCC clinical research staff will be assigned to this protocol. The responsibilities of the clinical research staff include project adherence, data collection, abstraction and entry, data reporting, regulatory monitoring, problem resolution and prioritization, and coordinating the activities of the protocol study team. Data gathered for this study will be obtained from enrolled patients by thoracic surgery providers, clinical research staff, clinical research nurse specialists. The data collected for this study will be entered into REDCap database to be accessed only by study staff. All data collected will be de-identified to maintain participants' confidentiality. Participants will be assigned unique identification numbers, which will be used to identify all the data. All participant related data will be identified only with a study code number. A list of the names and assigned identification number will be kept in a password protected log on the MSKCC share drive accessible only to relevant research staff.

Study findings will be presented in aggregate form only, with no reference made to individual participant's data. The Principal Investigator and their research team will be responsible for identifying, reviewing and reporting all necessary adverse events to the institutional IRB as appropriate. The data will be used specifically for the purposes outlined in this proposal and not for any other purpose. All study related documents and will be stored in a secure location until the study has ended and all data analyses are complete. At that time, all study material will be placed in a secured long-term storage facility until it is deemed appropriate to destroy the study material.

